5.2 Visit 1 Performance Analysis Set

The Visit 1 Performance Analysis Set comprises all members of the Enrolled Participant Analysis Set who did not withdraw and who completed an eDC questionnaire (V1eDC).

The Visit 1 Performance Analysis Set will be used for the analysis of Visit 1 eDC questionnaire data.

5.3 CVD IRT Performance Analysis Set

The CVD IRT Performance Analysis Set comprises all members of the Enrolled Participant Analysis Set who did not withdraw and for whom a valid CVD IRT report was generated.

The PRS Performance Analysis Set will be used for the analysis of CVD PRS and IRT performance.

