#### **7.1.11. Withdrawal criteria**

Participants may be withdrawn from the study at any time for any reason.

Reasons for withdrawal from the study may include, but are not limited to, the following:

- Participant's withdrawal of consent at any time.
- Investigator or Sponsor determines it is in the best interest of the patient.

Participants who wish to withdraw from the study can inform the investigator or study team at any time during the study. Participants who withdraw and who have had specimen samples taken for genetic analysis will not receive their results but their results will be used in the study analyses. A participant that wishes to withdraw before receiving the CVD IRT score will continue to receive their QRISK®2 score as per standard practice.

Reasonable effort will be made to obtain information about participants who withdraw from the study, and the primary reason for withdrawal/discontinuation documented.

The CRF will collect:

- date of withdrawal
- reason for withdrawal if the participant is willing to share.

As described in section 9.2, if a participant has an ongoing serious adverse device effect (SADE) or unanticipated SADE (USADE) at their final visit, follow-up to resolution should be attempted.

Patients who withdraw from the study will not be replaced.

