5 ANALYSIS SETS

5.1 Enrolled Participant Analysis Set

The Enrolled Participant Analysis Set will consist of all participants who have given consent and a blood sample taken.

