5.7 Saliva Performance Analysis Set

The Saliva Performance Analysis Set comprises all members of the Enrolled Participant Analysis Set who provided saliva samples.

The Saliva Performance Analysis Set will be used for the analysis of performance of data derived from saliva.

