| Secondary Objectives | | | |
| To explore and assess the impact of the CVD IRT on clinical decision-making | HCP feedback via questionnaires and focus groups | 
"TFLs_TOC_HEART_Example_layouts/DT2 2ry-1" (V2eDC-Q4, V2eDC-Q3, V2eDC-Q5, HCPQ-Q6, HCPQ-Q7, HCPQ-Q9, HCPQ-Q19, HCPQ-Q20)
 
"TFLs_TOC_HEART_Example_layouts/T10 HCPQual" (Comments relevant to objective compiled from free text responses to V2eDC-Q4, HCPQ-Q8, HCPQ-Q10, HCPQ-Q12, HCPQ-Q15 and HCPQ-Q24, and from HCP focus group discussions)
 | 
"TFLs_TOC_HEART_Example_layouts/T4 V2eDC-1" (HCP views summed over all participants processed)
 
"TFLs_TOC_HEART_Example_layouts/T5 V2eDC-2" (HCP views at start of study)
 
"TFLs_TOC_HEART_Example_layouts/T6 V2eDC-3" (HCP views at end of study)
 
"TFLs_TOC_HEART_Example_layouts/T8 HCPQ"
 |
| To assess the magnitude of the change in risk score between QRISK®2 and CVD IRT | QRISK®2 and CVD IRT scores to be compared | "TFLs_TOC_HEART_Example_layouts/DT3 2ry-2" | 
"TFLs_TOC_HEART_Example_layouts/T12 Risks"
 
"TFLs_TOC_HEART_Example_layouts/T13 Risk classification"
 
"TFLs_TOC_HEART_Example_layouts/T14 Deltas freq"
 
Ordered plot of deltas (CVD IRT minus QRISK®2) across individuals.
 |

| | | | |
|--|--|---|---|
| | | | Histograms of CVD IRT and QRISK®2 distributions, overall and split by age group, by sex, by ethnicity and by education level. |
| To explore and assess to what extent HCPs and PCCs perceive the CVD IRT as operationally efficient and enhancing the service that they provide | HCP feedback via questionnaires and focus groups | 
“TFLs_TOC_HEART_Example_lay outs/DT4 2ry-3” (V2eDC-Q6, HCPQ-Q3, HCPQ-Q5, HCPQ-Q11, HCPQ-Q14, HCPQ-Q16, HCPQ-Q17)
 
“TFLs_TOC_HEART_Example_lay outs/T10 HCPQual” (Comments relevant to objective compiled from free text responses in V2eDC, HCPQ and from HCP focus group discussions)
 | 
“TFLs_TOC_HEART_Example_lay outs/T4 V2eDC-1” (HCP views summed over all participants processed)
 
“TFLs_TOC_HEART_Example_lay outs/T5 V2eDC-2” (HCP views at start of study)
 
“TFLs_TOC_HEART_Example_lay outs/T6 V2eDC-3” (HCP views at end of study)
 
“TFLs_TOC_HEART_Example_lay outs/T8 HCPQ”
 |
| | PCC feedback via focus group | “TFLs_TOC_HEART_Example_lay outs/T11 PCCQual” (Comments relevant to objective compiled from PCC focus group discussions) | N/A |

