| | HCP feedback via questionnaires and focus groups | “TFLs_TOC_HEART_Example_layouts/DT8 2ry-7” (V2eDC-Q1, HCPQ-Q11, HCPQ-Q13, HCPQ-Q14, HCPQ-Q16, HCPQ-Q17, HCPQ-Q18) “TFLs_TOC_HEART_Example_layouts/T10 HCPQual” (Comments relevant to objective compiled from free text responses in HCPQ and from HCP focus group discussions) | “TFLs_TOC_HEART_Example_layouts/T4 V2eDC-1” (HCP views summed over all participants processed) “TFLs_TOC_HEART_Example_layouts/T8 HCPQ” |
| | PCC feedback via focus group | “TFLs_TOC_HEART_Example_layouts/T11 PCCQual” (Comments | N/A |

| | | | |
|---|--|---|---|
| | | relevant to objective compiled from PCC focus group discussions) | |
| 8 To evaluate the performance of saliva as compared to blood for use in the CVD IRT | QC data from saliva and blood samples (from the same individuals) | “TFLs_TOC_HEART_Example_layouts/DT9 2ry-8” | Additional analyses will be contained in the separate sample QC report. Ordered plot of deltas (CVD-IRT-from-saliva minus CVD-IRT-from-blood) across individuals in the Saliva Performance Analysis Set. |
| 9 To monitor the study for any potential safety concerns | Number and nature of adverse events recorded | “TFLs_TOC_HEART_Example_layouts/T16 Safety data” | |
| Exploratory Objectives | | | |
| 1 To explore and assess the perception of healthcare providers and commissioners on the usefulness of CVD IRT. | HCP and PCC feedback via questionnaires and focus groups | “TFLs_TOC_HEART_Example_layouts/T10 HCPQual” “TFLs_TOC_HEART_Example_layouts/T11 PCCQual” (Comments relevant to objective compiled from free text responses in V2eDC and HCPQ questionnaires, and from HCP and PCC focus group discussions) | N/A |
| 2 To collect further insights from the study which may aid in the development of clinical decision tools and products based on PRS for disease risk prediction. | HCP and participant feedback via questionnaires, interviews and focus groups | “TFLs_TOC_HEART_Example_layouts/T10 HCPQual” Comments relevant to objective compiled from free text responses in V2eDC, V3PartQ and HCPQ questionnaires, and from interviews and focus group discussions. | N/A |

Table 3: Performance analyses summary table.

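### SAP 5.3 removes everyone who withdrew from the PRS and IRT set, although protocol 7.1.11 says results of those who withdraw after sampling are used; the parent set of SAP 5.11 is undefined

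*SAP*

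**What the plan says.** **Protocol 7.1.11.** Participants who withdraw after samples have been taken for genetic analysis "will not receive their results but their results will be used in the study analyses". The next sentence of that paragraph begins "A participant that wishes to withdraw before receiving the CVD IRT score" and says that such a person still gets the QRISK®2 score. Those who withdraw are not replaced.

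**SAP 5.1.** The Enrolled Participant Analysis Set is "all participants who have given consent and a blood sample taken", with no condition on withdrawal.

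**SAP 5.3.** The CVD IRT Performance Analysis Set is "all members of the Enrolled Participant Analysis Set who did not withdraw and for whom a valid CVD IRT report was generated". Its use is then stated under another name: "The PRS Performance Analysis Set will be used for the analysis of CVD PRS and IRT performance".

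**SAP 5.2 and 5.4 to 5.6.** Each of these visit-based sets also excludes participants who withdrew.

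**SAP 5.7.** The saliva set is "all members of the Enrolled Participant Analysis Set who provided saliva samples", again with no condition on withdrawal.

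**SAP 5.11.** The Per Protocol set is drawn from a Performance Analysis Set with no qualifier. It admits people without a major violation who either completed the survey or withdrew before the PRS was delivered. It is for supportive analyses of selected endpoints.

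**SAP 7.5.** The objective 2 row (QRISK®2 against CVD IRT) points to the layout "TFLs_TOC_HEART_Example_layouts/DT3 2ry-2" and names no analysis set.

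**SAP 7.11.** No change from the protocol's analyses is declared.

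**The concern.** The protocol makes a commitment about data already collected: once a sample has been given, the genetic result enters the analyses even if the person leaves. The SAP section that defines the population for genetic and integrated risk performance removes those people, and the section meant for departures reports none. An analyst who follows SAP 5.3 produces a population that the protocol contradicts. An analyst who follows the protocol departs from the SAP.

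The Per Protocol definition has a related gap. It makes room for early withdrawals, but nearly every set it could be drawn from has already removed them. The set cannot be programmed from the text as it stands.

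What is at stake is a clear, pre-specified population, plus a small loss of precision.

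**Working it through.** **Step 1. Follow one participant through the sets.** Take someone who consents, gives blood, yields a valid genetic result and withdraws before Visit 2.

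| Source | Does this person's result count? |
|---|---|
| Protocol 7.1.11 | Yes, used in the analyses |
| SAP 5.1 Enrolled | Member |
| SAP 5.2 to 5.6, including 5.3 | Not a member |
| SAP 5.7 Saliva | Member only if a saliva donor |

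The SAP names the Enrolled set for safety (7.7) and summarises disposition for all enrolled participants (7.1). It does not assign that set to genetic results. For the roughly 1000 - 100 = 900 participants who are not saliva donors, no set that the SAP assigns to genetic results keeps the withdrawn person.

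**Step 2. How far the protocol rule reaches.** It speaks of people who will not receive their results, and the next sentence deals with withdrawal before the score is received. Withdrawal before results is clearly covered. Withdrawal after Visit 2 is not, because that person already has the result. The SAP 5.3 exclusion has no time limit and removes both groups. The conflict is established for the first group only.

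**Step 3. Candidate parents for SAP 5.11.**

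| Candidate parent | People who withdrew before PRS delivery |
|---|---|
| Any of 5.2 to 5.6 | None, because all who withdrew are excluded |
| 5.7 Saliva | Possible, but the set is limited to about 100 donors |
| 5.8 HCPQ | Not applicable, because it contains HCPs |

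The pre-lock memo in 5.11 settles violation and evaluability criteria, and the data review meeting in 7.10 allocates subjects to sets. Neither is said to name the parent.

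**Step 4. Size.** There is no figure in the plan to reproduce. Inputs:
- planned N = 1000 (protocol 10.1, SAP 3.4)
- withdrawal rate w, assumed to be 2-5% with a range of 1-10%; the protocol's attrition figure is not shown in the text supplied
- all 1000 assumed to have a valid result

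Number dropped = 1000 × w. Interval width is proportional to 1/√n, so the width of the 5.3 set relative to a set that keeps everyone is √(1/(1 − w)).

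| w | Dropped | Remaining | Relative width | 95% half-width at p = 0.5 (all 1000: 3.10 points) |
|---|---|---|---|---|
| 1% | 10 | 990 | √(1/0.99) = 1.0050 (+0.5%) | 3.11 |
| 2% | 20 | 980 | √(1/0.98) = 1.0102 (+1.0%) | 3.13 |
| 5% | 50 | 950 | √(1/0.95) = 1.0260 (+2.6%) | 3.18 |
| 10% | 100 | 900 | √(1/0.90) = 1.0541 (+5.4%) | 3.27 |

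Because the comparison set keeps all withdrawals, these figures do not depend on when people withdraw.

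If those who withdrew differed by d points on some proportion, leaving them out would move the estimate by w × d. At d = 10 this is 0.1, 0.2, 0.5 and 1.0 points for the four rates. The value of d is an illustration; nothing in the documents suggests one.

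**The case against.** **The protocol does not say which analyses will use the results.** It defines no analysis sets and leaves methods to the SAP (10.3), and the SAP does keep withdrawn participants in 5.1 and 5.7. The link from 5.3 to objective 2 is an inference, since the table row names no set and the appended layouts, which might name one, were not supplied. This limits what can be said about a particular endpoint. It does not remove the mismatch, because 5.3 is the set that the SAP assigns to PRS and IRT performance, and its exclusion is neither explained nor declared.

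**A reader might infer that the SAP contradicts itself on saliva.** The objective 8 display is "Ordered plot of deltas (CVD-IRT-from-saliva minus CVD-IRT-from-blood) across individuals in the Saliva Performance Analysis Set", so a withdrawn donor's blood score can count there but not in 5.3. The documents do not support calling this an error. Different objectives may use different sets, objective 8 is a within-person technical comparison, and 5.7 follows the protocol rule.

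**There is a route to repair before lock.** SAP 7.10 lists finalisation of the SAP among the tasks of the data review meeting held before the final analysis. That stands: the gap in 5.11 can be closed in time, and the set is supportive only. It is an opportunity to correct the text, and nothing in the SAP shows that the correction is planned.

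**The loss is visible.** SAP 7.1 reports formal withdrawals and tabulates reasons. This also stands, and it is one reason why the point is minor.

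**Conclusion.** Two faults hold. First, SAP 5.3 conflicts with protocol 7.1.11 for participants who withdraw before receiving results, and SAP 7.11 does not declare the departure. Second, SAP 5.11 rests on an undefined parent set, and its provision for early withdrawals is empty under 5.2 to 5.6. The use of PRS for CVD IRT in the second sentence of 5.3 is a naming slip with a plain meaning.

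Severity is minor. The study is single-arm and descriptive. Under the assumed 2-5% withdrawal, 20-50 of 1000 participants are dropped and intervals widen by 1.0-2.6%; over 1-10% the figures are 10-100 participants and 0.5-5.4%. These are upper counts for the established conflict, because some withdrawals may come after results.

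Two stronger readings are not supported. A reader might infer that the exclusion biases the risk comparison, but the documents give no withdrawal rate and no sign that those who leave differ in risk. A reader might also infer that the protocol requires everyone who ever withdraws to be kept, but its wording clearly reaches only those who have not yet received results.

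**What to change.** **SAP 5.3.** Delete the withdrawal condition. Define the set as enrolled participants with a valid CVD IRT result, whether or not a report was returned. Keying the set to the result matters because the SAP does not say whether a report is generated for someone who has left; removing the withdrawal words alone might not restore them. Use the name CVD IRT Performance Analysis Set in both sentences. This wording also keeps people who withdraw after results, which is a simplifying choice that protocol 7.1.11 does not clearly require.

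**SAP 5.11.** Name a defined parent set that does not exclude withdrawals, for example the corrected 5.3 set or the Enrolled Participant Analysis Set. The choice is the sponsor's.

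**If exclusion is intended.** Declare the departure in SAP 7.11 or amend protocol 7.1.11. SAP 5.11 still needs a named parent.

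**Cost.** A few words in the SAP before database lock, or one declared departure or protocol wording change. No new data are needed.

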5.4 Visit 2 Performance Analysis Set

The Visit 2 Performance Analysis Set comprises all members of the Enrolled Participant Analysis Set who did not withdraw and who attended Visit 2 and received a valid CVD IRT report, and for whom a Visit 2 HCP questionnaire (V2eDC) was completed.

The Visit 2 Performance Analysis Set will be used for the analysis of Visit 2 HCP questionnaire data.

5.5 Visit 3 Performance Analysis Set

The Visit 3 Performance Analysis Set comprises all members of the Enrolled Participant Analysis Set who did not withdraw and who completed the 'Visit 3' online participant questionnaire (V3PartQ).

The Visit 3 Performance Analysis Set will be used for the analysis of 'Visit 3' online participant questionnaire data.

5.6 Visit 4 Performance Analysis Set

The Visit 4 Performance Analysis Set comprises all members of the Enrolled Participant Analysis Set who did not withdraw and who completed the 'Visit 4' telephone interview.

The Visit 4 Performance Analysis Set will be used for the analysis of 'Visit 4' telephone interview data.

5.7 Saliva Performance Analysis Set

The Saliva Performance Analysis Set comprises all members of the Enrolled Participant Analysis Set who provided saliva samples.

The Saliva Performance Analysis Set will be used for the analysis of performance of data derived from saliva.

5.8 HCPQ Performance Analysis Set

The HCPQ Performance Analysis Set comprises all HCP individuals who completed the HCP questionnaire (HCPQ).

The HCPQ Performance Analysis Set will be used for the analysis of HCPQ questionnaire data.

5.9 HCP Focus Group Analysis Set

The HCP Focus Group Analysis Set comprises all HCP individuals who took part in the HCP focus group(s).

The HCP Focus Group Analysis Set will be used for the analysis of HCP focus group data.

5.10 PCC Focus Group Analysis Set

The PCC Focus Group Analysis Set comprises all PCC individuals who took part in the PCC focus group(s).

The PCC Focus Group Analysis Set will be used for the analysis of PCC focus group data.

5.11 Per Protocol Analysis Set

The Per Protocol Analysis Set comprises all Participants in the Performance Analysis Set who had no major protocol violation and either:

- Completed their Survey or
- Withdrawn before PRS delivered

All criteria for major protocol violations and patient evaluability for Per Protocol Analysis Set will be established by the study team prior to the database lock and will be documented in a memo by the study team. Supportive performance analyses will be performed for selected performance endpoints using the Per Protocol Analysis Set.

6 GENERAL STATISTICAL CONSIDERATIONS

Descriptive statistics on continuous variables will include the number of observations (n), mean, standard deviation (SD), 95% confidence interval, minimum, first quartile (Q1), median, third quartile (Q3), and maximum. Categorical variables, including categories which are created by combining sub-categories, will be summarised using the frequency count and percentage in each category, together with a 95% confidence interval.

All analyses will be performed using the R statistical software environment (version 4.1.2 or higher).

7 STATISTICAL ANALYSIS

Quantitative statistical analysis will be performed by Genomics plc. Qualitative summaries of focus group discussions will be provided by NECS.

7.1 Patient Disposition

Patient disposition information will be summarised for all enrolled Participants for the following disposition categories:

- Participants who were enrolled
- Participants who provided a sample
- Participants who completed a V3PartQ questionnaire
- Participants who completed a Visit 4 telephone interview

Participants who formally withdrew from the study

The primary reasons for terminating will be tabulated. The primary reason for early withdrawal from the study will also be tabulated.

In addition, the number and percentage of participants in each analysis set will be presented. All disposition data will be listed by patient.

7.2 Demographics and Baseline Characteristics

Demographics and baseline characteristics will be summarised descriptively for all analysis sets. These include age (in years), biological sex (male / female), age group (5-year age groups: 45-49 / 50-54 / 55-59 / 60-64), self identified ethnicity, and education level.

Self- identified ethnicity is reported in the following categories:

White: English, Welsh, Scottish, Northern Irish or British / Irish Gypsy or Irish Traveller / Other

Mixed/Multiple: White and Black Caribbean / White and Black African / White and Asian / Any other mixed ethnicity

Asian or Asian British: Indian / Pakistani / Bangladeshi / Chinese / Other Asian background

Black African, Black Caribbean or Black British: African / Caribbean / Other Black background

Other ethnic group: Arab / Other

Education level is reported in the following categories:

Early education: No formal qualifications / GCSE attained / EBacc

Further education: Vocational Training / Apprenticeship / BTech L3 / A Levels

Higher education: Undergraduate Degree / Postgraduate Degree

Categorical baseline variables (e.g., biological sex, age group, self identified ethnicity, education level), will be summarized by the number and percentage of participants in corresponding categories. Continuous baseline variables (e.g age at informed consent) will be summarised by descriptive statistics (number of observations, mean, standard deviation, median, Q1, Q3, minimum, and maximum).

All demographic and baseline characteristics data will be listed by patient.

7.3 Disease History, Medical History and Prior and Concomitant Medications

No information on disease history, medical history and prior and concomitant medications will be recorded as part of this study, unless recorded as part of interview and focus group feedback, and except for the implied lack of certain conditions (e.g. CVD-free) that arise from the study entry criteria. The underlying variables that make up the QRISK®2 score will not be recorded as part of this study.

7.4 Protocol Deviations

Protocol deviations will be categorised as 'major' or 'minor' at a data review meeting convened by the sponsor. All major deviations and selected minor deviations (including but not limited to violation of entry criteria) will be listed.

7.5 Performance Analyses Summary Table

The study objectives will be met from a combination of quantitative analyses (e.g. on risk scores, report generation times, and fixed-category questionnaire responses) and qualitative assessments (e.g. free-text questionnaire responses, interview responses, and focus group responses).

The following table describes the study objectives, and summarises the ways in which each objective will be met. Each objective will be met from a holistic assessment of a series of quantitative and qualitative analyses. Please refer to the appended Excel files “TFLs_TOC_HEART.xlsx” and “TFLs_TOC_HEART_Example_layouts” for further details on table layouts referred to below.

| Objectives | Data type | Key Tables/Metrics | Supporting Tables/Figures |
|---|--|---|--|
| Primary Objective | | | |
| To demonstrate that an integrated risk tool (combining genetic and non-genetic risk factors) for CVD can be incorporated into routine primary care. | Report return rate | “TFLs_TOC_HEART_Example_layouts/DT1 1ry” | “TFLs_TOC_HEART_Example_layouts/T1 Participant” “TFLs_TOC_HEART_Example_layouts/T15 Timings” Histogram of days til report returned |
| | Participant feedback via questionnaires (quantitative responses) | “TFLs_TOC_HEART_Example_layouts/DT1 1ry” (V1eDC-Q1, V3PartQ-Q9) | “TFLs_TOC_HEART_Example_layouts/T3 V1eDC” “TFLs_TOC_HEART_Example_layouts/T7 V3PartQ” |
| | Participant feedback via interviews and questionnaires (qualitative responses) | “TFLs_TOC_HEART_Example_layouts/T9 PartQual” (Comments relevant to objective compiled from free text responses in V3PartQ-Q3 and from telephone interviews) | N/A |
| | HCP feedback via questionnaires | “TFLs_TOC_HEART_Example_layouts/DT1 1ry” (V2eDC-Q6, HCPQ-Q3, HCPQ-Q5, HCPQ-Q14) | “TFLs_TOC_HEART_Example_layouts/T4 V2eDC-1” (HCP views summed over all participants processed) “TFLs_TOC_HEART_Example_layouts/T5 V2eDC-2” (HCP views at start of study) “TFLs_TOC_HEART_Example_layouts/T6 V2eDC-3” (HCP views at end of study) |

| | | | |
|---|--|--|---|
| | | | 
uts/T6 V2eDC-3" (HCP views at end of study)
 
"TFLs_TOC_HEART_Example_layouts/T8 HCPQ"
 |
| | HCP and PCC feedback via focus groups and questionnaires (qualitative responses) | 
"TFLs_TOC_HEART_Example_layouts/T10 HCPQual"
 
"TFLs_TOC_HEART_Example_layouts/T11 PCCQual"
 
(Comments relevant to objective compiled from free text responses to HCPQ-Q4, HCPQ-Q8, HCPQ-Q10 and HCPQ-Q15, and from HCP and PCC focus groups)
 | N/A |
| Secondary Objectives | | | |
| To explore and assess the impact of the CVD IRT on clinical decision-making | HCP feedback via questionnaires and focus groups | 
"TFLs_TOC_HEART_Example_layouts/DT2 2ry-1" (V2eDC-Q4, V2eDC-Q3, V2eDC-Q5, HCPQ-Q6, HCPQ-Q7, HCPQ-Q9, HCPQ-Q19, HCPQ-Q20)
 
"TFLs_TOC_HEART_Example_layouts/T10 HCPQual" (Comments relevant to objective compiled from free text responses to V2eDC-Q4, HCPQ-Q8, HCPQ-Q10, HCPQ-Q12, HCPQ-Q15 and HCPQ-Q24, and from HCP focus group discussions)
 | 
"TFLs_TOC_HEART_Example_layouts/T4 V2eDC-1" (HCP views summed over all participants processed)
 
"TFLs_TOC_HEART_Example_layouts/T5 V2eDC-2" (HCP views at start of study)
 
"TFLs_TOC_HEART_Example_layouts/T6 V2eDC-3" (HCP views at end of study)
 
"TFLs_TOC_HEART_Example_layouts/T8 HCPQ"
 |
| To assess the magnitude of the change in risk score between QRISK®2 and CVD IRT | QRISK®2 and CVD IRT scores to be compared | "TFLs_TOC_HEART_Example_layouts/DT3 2ry-2" | 
"TFLs_TOC_HEART_Example_layouts/T12 Risks"
 
"TFLs_TOC_HEART_Example_layouts/T13 Risk classification"
 
"TFLs_TOC_HEART_Example_layouts/T14 Deltas freq"
 
Ordered plot of deltas (CVD IRT minus QRISK®2) across individuals.
 |

| | | | |
|--|--|---|---|
| | | | Histograms of CVD IRT and QRISK®2 distributions, overall and split by age group, by sex, by ethnicity and by education level. |
| To explore and assess to what extent HCPs and PCCs perceive the CVD IRT as operationally efficient and enhancing the service that they provide | HCP feedback via questionnaires and focus groups | 
“TFLs_TOC_HEART_Example_lay outs/DT4 2ry-3” (V2eDC-Q6, HCPQ-Q3, HCPQ-Q5, HCPQ-Q11, HCPQ-Q14, HCPQ-Q16, HCPQ-Q17)
 
“TFLs_TOC_HEART_Example_lay outs/T10 HCPQual” (Comments relevant to objective compiled from free text responses in V2eDC, HCPQ and from HCP focus group discussions)
 | 
“TFLs_TOC_HEART_Example_lay outs/T4 V2eDC-1” (HCP views summed over all participants processed)
 
“TFLs_TOC_HEART_Example_lay outs/T5 V2eDC-2” (HCP views at start of study)
 
“TFLs_TOC_HEART_Example_lay outs/T6 V2eDC-3” (HCP views at end of study)
 
“TFLs_TOC_HEART_Example_lay outs/T8 HCPQ”
 |
| | PCC feedback via focus group | “TFLs_TOC_HEART_Example_lay outs/T11 PCCQual” (Comments relevant to objective compiled from PCC focus group discussions) | N/A |
| To explore and assess to what extent HCPs and PCCs perceive the CVD IRT as clinically relevant | HCP feedback via questionnaires and focus groups | 
“TFLs_TOC_HEART_Example_lay outs/DT5 2ry-4” (HCPQ-Q3, HCPQ-Q6, HCPQ-Q7, HCPQ-Q11, HCPQ-Q19, HCPQ-Q20, HCPQ-Q21)
 
“TFLs_TOC_HEART_Example_lay outs/T10 HCPQual” (Comments relevant to objective compiled from free text responses in HCPQ and from HCP focus group discussions)
 | “TFLs_TOC_HEART_Example_lay outs/T8 HCPQ” |
| | PCC feedback via focus group | “TFLs_TOC_HEART_Example_lay outs/T11 PCCQual” (Comments relevant to objective compiled from PCC focus group discussions) | N/A |
| 5 To explore and assess to what extent participants | Participant feedback via questionnaires and interviews | “TFLs_TOC_HEART_Example_lay outs/DT6 2ry-5” (V1eDC-Q4, V3PartQ-Q1, V3PartQ-Q2, | “TFLs_TOC_HEART_Example_lay outs/T3 V1eDC” |

| | | | |
|---|--|--|--|
| perceive the information received through the CVD IRT as informative for health and wellness | | V3PartQ-Q6, V3PartQ-Q9, V3PartQ-Q14) “TFLs_TOC_HEART_Example_layouts/T9 PartQual” (Comments relevant to objective compiled from free text responses in V3PartQ and from telephone interviews.) | “TFLs_TOC_HEART_Example_layouts/T7 V3PartQ” |
| 6 To explore and assess the impact of the CVD IRT on patient engagement | Participant feedback via questionnaires and interviews | “TFLs_TOC_HEART_Example_layouts/DT7 2ry-6” (V1eDC-Q4, V3PartQ-Q1) “TFLs_TOC_HEART_Example_layouts/T9 PartQual” (Comments relevant to objective compiled from free text responses in V3PartQ (in particular V3PartQ-Q13) and from telephone interviews) | “TFLs_TOC_HEART_Example_layouts/T3 V1eDC” “TFLs_TOC_HEART_Example_layouts/T7 V3PartQ” |
| 7 To identify and explore effective ways to communicate risk and genetics information about CVD IRT to patients, HCP and PCCs | Participant feedback via questionnaires and interviews | “TFLs_TOC_HEART_Example_layouts/DT8 2ry-7” (V1eDC-Q3, V1eDC-Q4, V3PartQ-Q4, V3PartQ-Q5, V3PartQ-Q6, V3PartQ-Q9, V3PartQ-Q14) “TFLs_TOC_HEART_Example_layouts/T9 PartQual” (Comments relevant to objective compiled from free text responses in V3PartQ and from telephone interviews) | “TFLs_TOC_HEART_Example_layouts/T3 V1eDC” “TFLs_TOC_HEART_Example_layouts/T7 V3PartQ” |
| | HCP feedback via questionnaires and focus groups | “TFLs_TOC_HEART_Example_layouts/DT8 2ry-7” (V2eDC-Q1, HCPQ-Q11, HCPQ-Q13, HCPQ-Q14, HCPQ-Q16, HCPQ-Q17, HCPQ-Q18) “TFLs_TOC_HEART_Example_layouts/T10 HCPQual” (Comments relevant to objective compiled from free text responses in HCPQ and from HCP focus group discussions) | “TFLs_TOC_HEART_Example_layouts/T4 V2eDC-1” (HCP views summed over all participants processed) “TFLs_TOC_HEART_Example_layouts/T8 HCPQ” |
| | PCC feedback via focus group | “TFLs_TOC_HEART_Example_layouts/T11 PCCQual” (Comments | N/A |

| | | | |
|---|--|---|---|
| | | relevant to objective compiled from PCC focus group discussions) | |
| 8 To evaluate the performance of saliva as compared to blood for use in the CVD IRT | QC data from saliva and blood samples (from the same individuals) | “TFLs_TOC_HEART_Example_layouts/DT9 2ry-8” | Additional analyses will be contained in the separate sample QC report. Ordered plot of deltas (CVD-IRT-from-saliva minus CVD-IRT-from-blood) across individuals in the Saliva Performance Analysis Set. |
| 9 To monitor the study for any potential safety concerns | Number and nature of adverse events recorded | “TFLs_TOC_HEART_Example_layouts/T16 Safety data” | |
| Exploratory Objectives | | | |
| 1 To explore and assess the perception of healthcare providers and commissioners on the usefulness of CVD IRT. | HCP and PCC feedback via questionnaires and focus groups | “TFLs_TOC_HEART_Example_layouts/T10 HCPQual” “TFLs_TOC_HEART_Example_layouts/T11 PCCQual” (Comments relevant to objective compiled from free text responses in V2eDC and HCPQ questionnaires, and from HCP and PCC focus group discussions) | N/A |
| 2 To collect further insights from the study which may aid in the development of clinical decision tools and products based on PRS for disease risk prediction. | HCP and participant feedback via questionnaires, interviews and focus groups | “TFLs_TOC_HEART_Example_layouts/T10 HCPQual” Comments relevant to objective compiled from free text responses in V2eDC, V3PartQ and HCPQ questionnaires, and from interviews and focus group discussions. | N/A |

Table 3: Performance analyses summary table.

